This study is an investigation of 97 subjects who have expressed interest in using CBD for anxiety. Subjects will complete study visits at McLean Hospital. Following a preliminary phone screen and prior to any evaluation, all study subjects will be required to sign a McLean Hospital approved informed consent form that describes all study procedures. The phone screen includes questions related to medical history, substance use history, demographics, and screening questions from the OASIS (see below) to determine whether the subject has anxiety.

Individuals will be assessed at baseline and weekly for four weeks of treatment with compounds administered as sublingual tinctures in a double-blind, randomized procedure: subjects will receive either a full-spectrum high CBD product, a single-compound CBD product, or matched placebo in a 3:1:1 randomization schedule. Each product will be analyzed and verified at an outside lab for safety and potency. Subjects will self-administer 1 ml (10mg/ml) of CBD or placebo sublingually three times daily. At each weekly visit, individuals will complete clinical scales and have a check-in with study staff. Neuropsychological testing will be performed at baseline and the final visit in order to assess cognitive performance. Buccal swabs will be collected for DNA analysis from all participants in the double-blind phase, and a subset of

individuals will complete blood draws at baseline and week 4 in order to assess levels of circulating endocannabinoids. Finally, a subset of individuals will receive an hour-long MRI scan at baseline and the final visit, with both resting state and task-related functional magnetic resonance imaging (fMRI) in each MRI session. In addition, a brief diffusion tensor imaging (DTI) sequence will also be acquired to examine white matter fiber tract integrity, and magnetic resonance spectroscopy (MRS) will be conducted to examine levels of certain metabolites in the brain.

At the investigators' discretion, in order to assess clinical state, participants may complete daily mood ratings either on paper or electronically via REDCap or StudyTrax. Additionally, subjects will be given the option to complete study drug diaries manually (pencil and paper) or via a secure web portal.

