In order to assess the efficacy of the dose chosen for the double-blind study, we will also conduct a small open-label phase I trial of the full-spectrum CBD tincture prior to initiating the double-blind study. This open-label trial will enroll up to 22 participants who are interested in using CBD, and who have anxiety. This trial will determine whether patients derive clinical benefits at the current dosage proposed for the active treatment arm of the double-blind trial. This trial will examine all components of the originally proposed study. During the open-label phase, a subset of participants (up to n=16) will complete an extra visit that includes clinical rating scales and a 2-hour continuous blood draw directly following administration of the tincture in order to assess plasma concentration of CBD over time and correlation with anxiety.

Subjects will be recruited through IRB-approved advertisements and flyers in regions that have approved medical marijuana. Additionally, medical marijuana healthcare facilities throughout New England, including CannaCare, Integr8, MMJ Physician Practice, and others, may also refer interested patients to contact the study recruitment line for further screening. These healthcare groups provide their interested patients who meet for general inclusion criteria with study recruitment materials. The total sample size for the double-blind study is 75 (45 full-spectrum CBD, 15 single-compound CBD, and 15 placebo); up to 15 of each group (45 total) will also complete the MRI scanning protocol. For the open-label trial, the total sample size is 16 (we will enroll up to 22 to ensure 16 completers); up to 16 subjects will complete the MRI scanning protocol.

Inclusion Criteria

- 1) Subject has provided informed consent
- 2) Subject is 18 or older
- 3) Subject is a native English speaker or acquired English prior to age 5
- 4) Subject scores a minimum of 16 on the Beck Anxiety Inventory (BAI) OR a minimum of 11 on the Overall Anxiety Severity and Impairment Scale (OASIS) at the screening/baseline visit or at phone screening if within 2 weeks of the baseline visit

Exclusion Criteria

Subjects will be excluded if they report any of the following:

- 1) Non-native English speakers
- 2) Estimated IQ < 75
- 3) Meets criteria for DSM-V classification of current substance abuse/dependence, a psychotic disorder, bipolar disorder, or an eating disorder

- 4) A history of head injury or loss of consciousness greater than 5 minutes

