Standard of care for anxiety treatment includes medications, such as antidepressants, buspirone, and benzodiazepines, as well as psychotherapy. This study is an investigation of a plant-derived compound that has promise in the treatment of anxiety. Subjects will not be asked to change their current treatment regimen to participate in this study (i.e. discontinue other medications); this study will add CBD to their current regimen.

Describe how risks to subjects are minimized, for example, by using procedures which are consistent with sound research design and which do not unnecessarily expose subjects to risk or by using procedures already being performed on the subject for diagnostic or treatment purposes.

Risks to subjects will be minimal throughout this study; please see below for detailed explanation of foreseeable risks and discomforts. The components of this study, including the clinical rating scales, neurocognitive tasks, and MR scanning have previously been used by the investigator in multiple studies. The administration of CBD will be low risk due to the add-on design of the study; patients will proceed with their treatment as usual, with CBD or placebo added to their medication regimen. See below for a detailed explanation of the risks of CBD administration in this population.

Describe explicitly the methods for ensuring the safety of subjects. Provide objective criteria for removing a subject from the study, for example, objective criteria for worsening disease/lack of improvement and/or unacceptable adverse events. The inclusion of objective drop criteria is especially important in studies designed with placebo control groups.

The side-effect profile of CBD is extremely low, and adverse events are not anticipated. Subjects may withdraw from the study at any time and for any reason. A subject's participation in the trial will end if they report adverse effects of CBD or placebo administration and wish to leave the study, or if study staff determine that study termination is appropriate due to adverse events.

FORESEEABLE RISKS AND DISCOMFORTS

Provide a brief description of any foreseeable risks and discomforts to subjects. Include those related to drugs/devices/procedures being studied and/or administered/performed solely for research purposes. In addition, include psychosocial risks, and risks related to privacy and confidentiality. When applicable, describe risks to a developing fetus or nursing infant.

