Walsh, Z. et al. (2013). Cannabis for therapeutic purposes: patient characteristics, access, and reasons for use. *Int J Drug Policy* 24(6), 511-516

Zhornitsky, S., & Potvin, S. (2012). Cannabidiol in humans – the quest for therapeutic targets.

Zuardi, A.W. et al. (2009). Cannabidiol for the treatment of psychosis in Parkinson's disease. *Journal of Psychopharmacology*, 23, 979-983

Statistical Approaches

All statistical analyses will be conducted using IBM SPSS Statistics (version 25). Data will be screened for outliers (defined as outside 1.5x the interquartile range), skew, kurtosis, non-normality, and homogeneity of variance. If the assumptions of parametric inferential analyses are not met, the appropriate non-parametric analyses will be performed. Baseline demographic, clinical, and neuropsychological data will be assessed using 2-tailed analyses of variance (ANOVAs). Treatment effects over the course of the study will be assessed using mixed model ANOVAs with Scheffe post hoc tests utilized to assess between-group differences and Least Significant Difference (LSD) post hoc tests utilized to assess change over time (repeated-measures). Independent *t*-tests will be conducting for each individual treatment arm to assess post hoc differences between baseline data relative to post-treatment data. In order to observe small-to-medium effect interaction effect sizes ($f=.20$) with 85% statistical power with alpha set at .05, it is estimated that the sample size should be at least 45 participants.

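### With no missing-data rule, the planned mixed model ANOVA most naturally reads as a completers-only analysis of the weekly anxiety scales, and the double-blind phase has no dropout allowance

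*Combined protocol and SAP*

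**What the plan says.** The analysis plan is the single paragraph headed Statistical Approaches at the end of the document. On software: "All statistical analyses will be conducted using IBM SPSS Statistics (version 25"). On the model: "Treatment effects over the course of the study will be assessed using mixed model ANOVAs". The follow-up comparisons are of two kinds, one across arms and one across visits: "Scheffe post hoc tests utilized to assess between-group differences and Least Significant Difference (LSD) post hoc tests utilized to assess change over time (repeated-measures"). The size calculation targets an interaction effect of f = 0.20, and its error rates are given as follows: "with 85% statistical power with alpha set at .05". The resulting minimum is a total and not a figure per arm: "it is estimated that the sample size should be at least 45 participants". The paragraph names no SPSS procedure, no analysis population, no rule for missing visits and no dropout rate.

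Research Design and Methods sets five visits, with clinical scales at baseline and at each of four weekly visits. Neuropsychological testing takes place at baseline and the final visit only, as do the optional MRI scans; the double-blind blood draws are at baseline and week 4. Background and Significance places anxiety scales among the main outcomes.

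The two phases treat loss differently. On the open-label phase: "For the open-label trial, the total sample size is 16 (we will enroll up to 22 to ensure 16 completers"). The double-blind phase is 75, split 45 full-spectrum, 15 single-compound and 15 placebo. The overall count leaves no room for more: "This study is an investigation of 97 subjects who have expressed interest in using CBD for anxiety", and 97 = 75 + 22. Withdrawal is allowed at any time for any reason, and the plan adds that a person's "participation in the trial will end if they report adverse effects of CBD or placebo administration and wish to leave the study".

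**The concern.** A classical repeated-measures ANOVA needs a complete row of visits for each participant. Someone with baseline and weeks 1 to 3 but no week 4 drops out of the model altogether, and so does someone who misses only week 2. Two things follow for the weekly anxiety scales.

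- **Precision.** Data already collected are thrown away. The cost falls hardest on comparisons with the placebo arm, which starts at 15.
- **Bias.** The comparison is no longer between the groups as randomised. If people leave because of poor tolerability or lack of benefit, and do so differently by arm, the completers are not comparable.

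There is also a matter of pre-specification. With no rule written down, the handling of missing visits could be settled after the data are seen.

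**Working it through.** **1. The plan's own figure.** For a within-between interaction, λ = f²·N·m/(1−ρ), with df1 = (k−1)(m−1) and df2 = (N−k)(m−1). Take f = 0.20, k = 3 arms and m = 5 visits. The documents do not give ρ; assume ρ = 0.5 and sphericity.

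At N = 45, λ = 0.04 × 45 × 5/0.5 = 18.0 with df 8 and 168, and power is 0.861. The smallest N reaching 85% is 44, or 45 in equal arms of 15. So the stated 45 is reproduced by a three-arm, five-visit repeated-measures ANOVA. This is not unique: two visits with ρ = 0.7 also gives 45.

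**2. Allowance for loss.**
- Open-label: (22 − 16)/22 = 27.3%. This is an upper limit, since the plan enrols up to 22.
- Double-blind: 97 − 22 = 75, exactly the planned size, so the allowance is zero.

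**3. Completers if the double-blind phase lost the same share (scenario).**
- Full-spectrum: 45 × 16/22 = 32.7
- Single-compound and placebo: 15 × 16/22 = 10.9 each
- Total: 75 × 16/22 = 54.5

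At assumed losses of 10%, 20% and 30%, placebo would be 13.5, 12.0 and 10.5.

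**4. Precision with completers only.** The standard error rises by √(22/16) = 1.173, or 17%. Detectable difference by two-sample t-test (noncentral t, two-sided 0.05, 85% power):

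| Comparison | As planned | At 16/22 completion |
|---|---|---|
| Full-spectrum v placebo | 0.91 SD (45 v 15) | 1.07 SD (33 v 11) |
| Single-compound v placebo | 1.13 SD (15 v 15) | 1.34 SD (11 v 11) |

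**5. How much of that a mixed model recovers.** Take the final-visit arm contrast, adjusted for baseline, with known covariance and the 27.3% loss spread equally over the four post-baseline visits. Summing the information over dropout patterns gives these standard errors relative to no dropout:

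| Assumed covariance | Mixed model | Completers only |
|---|---|---|
| Compound symmetry, 0.5 | 1.15 | 1.17 |
| Compound symmetry, 0.7 | 1.14 | 1.17 |
| Autoregressive, 0.7 | 1.14 | 1.17 |
| Autoregressive, 0.8 | 1.13 | 1.17 |

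If everyone who leaves does so before week 1, there is no gain. If everyone misses only week 4, the rise is 8–14%.

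**6. Scattered missed visits.** Assume visits are missed independently; real dropout makes misses correlated.
- 5% missed per post-baseline visit: 0.95⁴ = 0.815, so 61 of 75 are complete. The completers' standard error rises by 1/√0.815 = 1.11. Using every available final-visit value gives 1/√0.95 = 1.03.
- 10% per visit: 0.90⁴ = 0.656, so 49 of 75 are complete, with 1/√0.656 = 1.23 against 1/√0.90 = 1.05.

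A mixed model should do no worse than the available-value figures, so this is where most of its precision gain lies.

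**The case against.** **The deletion rule is not written.** This stands. The plan names no SPSS procedure, and the phrase it uses could be stretched to a likelihood-based mixed model, which keeps partial data. The classical reading is an inference from the ANOVA wording, the pairing of Scheffe and repeated-measures LSD tests, and the Cohen's f power statement. The reproduced 45 supports it without settling it.

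**The trial is larger than it needs to be.** Partly right. About 55 completers exceed the stated 45, and on the equal-group formula in step 1 the five-visit interaction would still have power 0.93. But all 30 participants above 45 are in the full-spectrum arm. On an equal-arm reading, 45 means 15 per arm, so the placebo and single-compound arms have no margin.

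**27% is borrowed from another phase.** Also right. It is a ceiling chosen to secure 16 completers. A reader might infer that the plan expects 11 on placebo; the documents give no dropout rate for the double-blind phase.

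**The 17% is the price of dropout, not of ANOVA.** Largely right, as step 5 shows. A reader might infer that changing the model restores the precision in step 4. It would not.

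**Five-visit deletion is limited in scope.** It applies to the weekly scales. For outcomes measured only at baseline and week 4 or the final visit, someone without the second measurement has no post-baseline value, and a mixed model recovers little or nothing.

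**Dropout from adverse effects is not shown.** The plan does not anticipate adverse events and allows withdrawal for any reason. Differential dropout is possible, not demonstrated.

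**Conclusion.** The point holds in a limited form. The plan specifies neither how missing visits are handled nor who is analysed, and its wording most naturally describes a complete-case repeated-measures ANOVA. On the weekly anxiety scales that would discard partial data and expose the arm comparison to completer bias. Double-blind enrolment has no dropout allowance. At the open-label ceiling, about 33/11/11 would complete, which still meets the stated total but leaves placebo below 15.

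The documents do not support two stronger conclusions: that the plan states it will drop anyone with a missed visit, or that the trial as a whole falls short of its stated size.

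Replacing the model has three benefits: it keeps partial data, tolerates scattered missed visits and reduces completer bias. Its gain in standard error under evenly spread 27% dropout is small, a rise of about 13–15% instead of 17%. Those figures rest on assumed covariances and dropout patterns, and the size of any bias cannot be derived from the documents. The change is worth making before unblinding because it is cheap and removes a choice that is now open.

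**What to change.** In Statistical Approaches, for the weekly clinical scales:

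1. Define the analysis population as all randomised participants, analysed in the arm to which they were randomised.
2. Replace the ANOVA with a likelihood-based mixed model for repeated measures (SPSS MIXED) with arm, visit, arm-by-visit and baseline, an unstructured covariance, and every available visit. State the comparison with placebo that carries the conclusion.
3. Replace the Scheffe tests with model-based contrasts and a named multiplicity adjustment.
4. Add one sensitivity analysis for data not missing at random, for example assuming that participants who leave a CBD arm do no better than placebo afterwards.
5. Give the expected completers per arm beside the 75, under a stated dropout assumption. At 27% these are about 33/11/11.
6. For outcomes measured only at baseline and week 4 or the final visit, say that participants without the second measurement contribute little, and report their number by arm.

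The cost is SAP wording and slightly more analysis work, with no new data or participants. These steps do not restore numbers. Keeping 45/15/15 completers at 27% loss would need 15 ÷ (16/22) = 20.6, rounded to 21 per small arm, or 105 randomised (63/21/21). Whether to enrol more is a separate decision for the sponsor.

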Despite the recent interest in cannabinoid-based products, no published studies to date have conducted a clinical trial of products high in CBD in individuals who suffer from anxiety. Further, none have systematically evaluated baseline and follow-up clinical state and related quality of life measures in individuals taking CBD, or assessed measures of brain structure and function before and after treatment with CBD using neuropsychological measures or neuroimaging. As a growing number of states are legalizing medical marijuana and increasing evidence suggests that CBD may exert anxiolytic effects, there is a gap in the literature regarding the effects of CBD, often found in higher levels in medical marijuana than recreational marijuana, on anxiety. This investigation will be the first of its kind to conduct a double-blind clinical trial of high-CBD compounds (both full-spectrum and single-compound) in individuals with anxiety. The main outcome measures of the project will include a comprehensive assessment of anxiety using both self-report and administered scales pre- and post-treatment, as well as range of quality of life measures. In addition, this project will examine the impact of high CBD products relative to placebo on several cognitive domains using neuropsychological testing. Furthermore, a subset of eligible participants will complete a structural and functional MRI scanning to assess brain function and connectivity using a multimodal neuroimaging protocol prior to and following four weeks of treatment with high CBD compounds vs placebo.

RESEARCH DESIGN AND METHODS

Briefly describe study design and anticipated enrollment, i.e., number of subjects to be enrolled by researchers study-wide and by Partners researchers. Provide a brief summary of the eligibility criteria (for example, age range, gender, medical condition). Include any local site restrictions, for example, "Enrollment at Partners will be limited to adults although the sponsor's protocol is open to both children and adults."

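### Scheffe is valid for the three-arm comparison but stricter than pairwise questions need: it costs up to about 4 points of power against Tukey-Kramer and about 10 against Dunnett

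*Combined protocol and SAP*

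**What the plan says.** Research Design and Methods gives the arms: "The total sample size for the double-blind study is 75 (45 full-spectrum CBD, 15 single-compound CBD, and 15 placebo", randomized 3:1:1.

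Statistical Approaches assesses treatment effects over the study by "mixed model ANOVAs with Scheffe post hoc tests utilized to assess between-group differences". LSD tests are planned for change over time, and t-tests for change within each arm. The only power statement concerns an interaction effect of f = .20, "with 85% statistical power with alpha set at .05", from which "it is estimated that the sample size should be at least 45 participants". No effect size or power is given for any difference between two arms.

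The arm question is put in general terms. Background and Significance says "this project will examine the impact of high CBD products relative to placebo on several cognitive domains", without saying whether the two products are to be compared with placebo separately or pooled. No follow-up contrast is ranked above another.

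**The concern.** Scheffe suits an analyst who wants to test any contrast, including one suggested by the data. A three-arm trial with a placebo usually has a shorter list, known in advance: two comparisons with placebo, or three pairs. For such a list Scheffe's critical value is larger than a joint 5% error requires, and its confidence intervals are correspondingly wide.

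The loss falls where the design is weakest. Placebo and single-compound have 15 people each, so every pairwise comparison includes an arm of 15, and power for these comparisons is modest before any adjustment is chosen.

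**Working it through.** **Inputs.** From the documents: arms of 45/15/15, so N = 75 and error df = 75 − 3 = 72; alpha .05; Scheffe for arm differences; five assessments (baseline plus four weekly visits). Assumed: two-sided arm comparisons, because two-tailed testing is stated only for the baseline data ("will be assessed using 2-tailed analyses of variance (ANOVAs"); standardized differences d, because the documents give none; and a one-way comparison of arm means with common variance and no dropout.

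**1. The plan's own figure.** Within-between interaction, k = 3 arms, m = 5 visits, assumed within-subject correlation ρ = 0.5, sphericity:
- λ = N·f²·m/(1 − ρ) = 45 × 0.04 × 5/0.5 = 18.0
- df = (3 − 1)(5 − 1) = 8 and (45 − 3)(5 − 1) = 168
- Power = 86.1%. The smallest N reaching 85% is 44, or 45 as a multiple of three.

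The stated 45 is reproduced. It depends on ρ (N = 61 at ρ = 0.3, 28 at ρ = 0.7), and it describes the interaction, not the arm comparisons below.

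**2. Critical |t| at joint two-sided .05, 72 df.**
- Scheffe: √(2 × F(.95; 2, 72)) = √(2 × 3.124) = 2.50
- Tukey-Kramer, three pairs: q(.95; 3, 72)/√2 = 3.384/1.414 = 2.39
- Dunnett, two placebo comparisons: bivariate t with correlation √(45/60 × 15/30) = √0.375 = 0.61, giving 2.24

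Scheffe intervals are therefore wider by 2.4996/2.3931 = 1.044 (about 4%) than Tukey-Kramer and by 2.4996/2.2398 = 1.116 (about 12%) than Dunnett.

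**3. Error rate that Scheffe actually uses.** Each comparison alone: 1.5%. The two placebo comparisons jointly: 2.7%, by numerical integration and by 1,000,000 simulated trials. All three pairs jointly: 3.8%, by simulation.

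**4. Power.** Noncentral t, 72 df, noncentrality d/√(1/n₁ + 1/15). The denominator is 0.298 for full-spectrum (n₁ = 45) and 0.365 for single-compound (n₁ = 15). At d = 0.8 the noncentrality is 2.68 and 2.19.

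| Comparison with placebo | assumed d | Scheffe | Tukey-Kramer | Dunnett |
|---|---|---|---|---|
| Full-spectrum | 0.6 | 32% | 36% | 41% |
| Full-spectrum | 0.8 | 57.5% | 61.5% | 67.1% |
| Full-spectrum | 1.0 | 80% | 83% | 87% |
| Single-compound | 0.8 | 38.5% | 42.5% | 48.4% |
| Single-compound | 1.0 | 60% | 64% | 69% |

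Over all d, the largest gap is 4.1 points against Tukey-Kramer and 10.1 against Dunnett. The Dunnett gap peaks at d = 0.71 for full-spectrum (45.7% against 55.8%) and d = 0.87 for single-compound (45.8% against 55.9%).

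**5. Sensitivity.** With arms of 15/15/15, 25/25/25 or 27/9/9, the joint error over the two placebo comparisons stays at 2.7–2.8% and the largest loss against Dunnett at 9.5–10.2 points. Against Bonferroni for two comparisons (|t| 2.29) the largest loss is 8.2 points.

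**The case against.** The best defence is that Scheffe does what it promises. It holds 5% jointly over all contrasts, including pooled CBD against placebo, which the general wording about CBD products leaves open. Neither Dunnett on two comparisons nor Tukey-Kramer on three pairs covers that contrast. Where contrasts have not been ranked, Scheffe is also the method that protects against choosing one after seeing the data. This stands: the strictness buys something, and the criticism applies only if the arm questions are pairwise.

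It also stands that the 10-point figure depends on restricting the family to two placebo comparisons. If full-spectrum against single-compound is wanted as well, the loss is about 4 points.

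Three stronger readings are tempting but unsupported:
- *Scheffe contradicts the stated alpha, or runs each comparison at 2.7%.* The .05 belongs to the interaction power statement, Scheffe respects 5% over its own family, and 2.7% is a joint rate. No false-positive inflation arises from this choice.
- *The plan has no lead test.* The interaction is the only effect it powers, and the arm comparisons are post hoc to it. The interaction is not labelled primary, but it is the natural reading. What is missing is a list of follow-up contrasts, which is a gap in detail.
- *The trial has 57.5% power for full-spectrum against placebo.* That rests on an assumed d and a simplified analysis. The documents do not say which means Scheffe compares, whether averaged over visits or at week 4.

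Requiring a significant one-way F for arm means before testing would not rescue or worsen Scheffe: a significant Scheffe contrast already implies that F is significant.

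**Conclusion.** The point holds as a loss of efficiency, not an error of validity. For pairwise arm differences Tukey-Kramer gives narrower intervals than Scheffe for every pair at the same family-wise .05, and Dunnett gains more if only the placebo comparisons matter.

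The critical values and error rates follow from the planned arm sizes and do not depend on any assumed effect. The power losses vary with d, so the maxima are the safest summary. The absolute powers are illustrations under the stated assumptions, and they do not require the interaction to be significant first. The gain is modest, but it falls on the smallest arms and needs only a change of wording.

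**What to change.** In Statistical Approaches, keep the group-by-time interaction as the overall test. Replace Scheffe with Dunnett's test of full-spectrum against placebo and single-compound against placebo, at two-sided family-wise .05, with Dunnett-adjusted confidence intervals. If all three pairs are wanted, use Tukey-Kramer with its matching intervals instead. State which means are compared.

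The cost is a few words and no new participants or data. The small downside is that pooled CBD against placebo leaves the error-controlled family and is reported as supportive; under Dunnett the same applies to full-spectrum against single-compound. If the investigators do want the pooled contrast protected, they should say so, since that would be a reason to keep Scheffe.

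Make the change before the treatment codes are opened. If they are already open, disclose the new method as chosen post hoc.

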Official Title: Sublingual Cannabidiol for Anxiety

Principal Investigator: [name], Ph.D.

NCT Number: NCT02548559

Document Date: 01/21/2025

PARTNERS HUMAN RESEARCH COMMITTEE PROTOCOL SUMMARY

Answer all questions accurately and completely in order to provide the PHRC with the relevant information to assess the risk-benefit ratio for the study. Do not leave sections blank.

PRINCIPAL/OVERALL INVESTIGATOR

[name].

PROTOCOL TITLE

Sublingual Cannabidiol for Anxiety

FUNDING

Sundry Funds/Department

VERSION DATE

1/21/2025

SPECIFIC AIMS

Concisely state the objectives of the study and the hypothesis being tested.

This investigation is designed to examine how the impact of the administration of sublingual high-cannabidiol (CBD) compounds on individuals with anxiety disorders.

Specific Aim 1: To assess pre- and post-CBD treatment clinical state ratings of anxiety and quality-of-life ratings in individuals with anxiety disorders.

Specific Aim 2: To assess pre- and post-CBD treatment performance on a range of neurocognitive measures designed to examine cognitive function.

Specific Aim 3: In a subset of individuals, to examine structural and functional changes that may occur in the brain following treatment with CBD using magnetic resonance imaging (MRI).

Exploratory Aim: In a subset of individuals, to examine the pharmacokinetics and pharmacodynamics (PK/PD) of this CBD tincture via continuous blood draw.

Exploratory Aim: In a subset of individuals, to assess potential changes in circulating endocannabinoids pre- and post-CBD treatment.

BACKGROUND AND SIGNIFICANCE

Provide a brief paragraph summarizing prior experience important for understanding the proposed study and procedures.

Cannabis has been used for medicinal purposes across many cultures for a range of disorders dating as far back as 4000 BC. The flowering plant has been used to treat a wide range of maladies due to its effects on both physical and psychological conditions. The plant is comprised of phytocannabinoids, terpenoids, flavonoids, steroids and enzymes, the concentrations of which vary depending on the strain; the phytocannabinoids are the most cannabis-specific of these components, and bind to receptors typically modulated by endogenous cannabinoids (Zhornitsky

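### Ungated within-arm tests in arms of 45 and 15, with no primary outcome or decision rule, can show full-spectrum CBD improving and placebo not when both changed equally

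*Combined protocol and SAP*

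**What the plan says.** Statistical Approaches sets out three layers of testing for treatment response:

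- Between arms: "mixed model ANOVAs with Scheffe post hoc tests utilized to assess between-group differences".
- Over time: "Least Significant Difference (LSD) post hoc tests utilized to assess change over time (repeated-measures").
- Within each arm: "Independent *t*-tests will be conducting for each individual treatment arm", comparing baseline with post-treatment data.

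Research Design and Methods gives the arm sizes: "The total sample size for the double-blind study is 75 (45 full-spectrum CBD, 15 single-compound CBD, and 15 placebo"). Assessments are at baseline and at four weekly visits.

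On outcomes, Background and Significance says: "The main outcome measures of the project will include a comprehensive assessment of anxiety using both self-report and administered scales pre- and post-treatment". It adds a set of quality-of-life measures and several cognitive domains. Specific Aim 1 is framed within treatment, without mention of placebo: "To assess pre- and post-CBD treatment clinical state ratings of anxiety and quality-of-life ratings in individuals with anxiety disorders".

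Entry depends on a raised score: "Subject scores a minimum of 16 on the Beck Anxiety Inventory (BAI) OR a minimum of 11 on the Overall Anxiety Severity and Impairment Scale". That score may be taken at the screening/baseline visit itself, or by phone within the two weeks before baseline.

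The document names no primary outcome. It gives no correction across scales or visits, no condition that must be met before the within-arm tests are read, and no statement of which test decides efficacy.

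**The concern.** A significant fall in one arm and a non-significant fall in another is not evidence that the arms differ. With 45 people in one arm and 15 in the other, the larger arm reaches significance much more easily for the same true change. The misleading pattern therefore favours full-spectrum CBD.

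Some improvement common to all arms is plausible here. Participants enter on a high anxiety score that can also serve as their baseline, so regression to the mean and placebo response act in every arm. Existing treatment also continues throughout.

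The plan is strict between arms (Scheffe) and lenient within arms (LSD and per-arm t-tests), although only the between-arm comparison is controlled. A report could follow the plan exactly and still present within-arm improvement as benefit when placebo changed by the same amount.

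**Working it through.** **Inputs from the document.** Arms of 45, 15 and 15; five assessments; alpha .05; interaction effect f = .20; power 85%; stated minimum sample 45.

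**Assumptions.** Two-sided .05 for the post hoc tests (two-tailed testing is stated only for the baseline ANOVAs). The shared standardised change, dz = mean change / SD of change, is not given and is varied from 0 to 1.0. The number of scales is not given, so the figures are per scale.

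**Step 1: the plan's own figure.** For a repeated-measures group-by-time interaction, λ = f²·N·m/(1−ρ), with df (k−1)(m−1) and (N−k)(m−1). With k = 3 arms, m = 5 visits, N = 45 and an assumed ρ = .5 and sphericity:

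λ = .04 × 45 × 5 / .5 = 18, df = 8 and 168, power = .861.

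The stated 45 is therefore reproducible (N = 44 just reaches .85; 45 allows equal arms). It concerns the interaction with equal arms. It does not cover a 45 v 15 contrast.

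**Step 2: the misleading pattern under equal change.** The power of a paired test in the direction of improvement is P(n) = Pr[T(n−1, dz·√n) > t(.975, n−1)], with T noncentral t. The arms are independent, so the chance that full-spectrum is significant and placebo is not is P(45) × [1 − P(15)].

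| dz | P(45) | P(15) | Pattern |
|---|---|---|---|
| 0 | .025 | .025 | .02 |
| 0.2 | .26 | .11 | .23 |
| 0.3 | .50 | .19 | .41 |
| 0.4 | .75 | .30 | .52 |
| 0.5 | .907 | .438 | .51 |
| 0.6 | .98 | .58 | .41 |
| 0.8 | .999 | .82 | .18 |
| 1.0 | 1.00 | .95 | .05 |

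For example, at dz 0.5: .907 × (1 − .438) = .51.

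The reverse pattern, placebo significant and full-spectrum not, is at most about .10. With equal arms the pattern is P(1−P), which cannot exceed .25, so the 45 v 15 split about doubles the peak. Pooled-error LSD in a simulated three-arm, five-visit design gives a similar curve: .23, .50, .47, .135 and .03 at dz 0.2, 0.4, 0.5, 0.8 and 1.0.

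The plan's wording is an independent t-test, although baseline and post-treatment data come from the same people. That is a separate flaw. Taken literally with ρ = .5, it gives .715 × (1 − .197) = .57 at 0.5 and peaks at .61 at 0.6. It moves the peak and does not remove the pattern.

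**Step 3: the contribution of unadjusted LSD.** With no true change and no omnibus gate, any of the 4 comparisons with baseline is significant in about 16% of cases per arm and scale (simulated, five visits, ρ = .5).

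**Step 4: whether adjusting the within-arm tests cures it.** At alpha .0125 (Holm's first step over four contrasts):

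- dz 0.5: .769 × (1 − .220) = .60, up from .51.
- dz 0.8: .996 × (1 − .600) = .40, up from .18.
- dz 0.2: .114 × (1 − .036) = .11, down from .23.

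A stricter alpha costs the 15-person arm more power than the 45-person arm, so at moderate or large shared changes the pattern becomes more common.

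**Step 5: what a between-arm rule does.** Under equal change, the direct full-spectrum v placebo contrast is falsely significant in 5% of trials per scale at every dz. If the within-arm pattern counts only when the interaction has p < .05, it appears in 0.3% to 2.3% per scale.

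**Step 6: power of that contrast.** For a difference of 0.5 SD of change, 0.5 × √(45 × 15/60) = 1.677, and Pr(Z > 1.96 − 1.677) ≈ 39%.

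**The case against.** The plan does compare arms. It assigns treatment effects to the mixed ANOVA, its sample size targets the interaction, and it uses Scheffe between groups. Nowhere does it say that arms will be compared through their separate p-values, so it would be wrong to infer that the investigators intend to claim efficacy that way. This stands. What is missing is the rule that would prevent it.

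The rates depend on a shared change that the documents do not state. This also stands: at no change or at 1.0 the pattern is uncommon. Figures near 50% belong to the middle of the range.

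Four stronger readings are tempting and are not supported:

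- *Improvement in the CBD arms is nearly assured.* This fits only the 45-person arm, and only at changes of about 0.5 or more. The 15-person single-compound arm has paired-test power of .44 at 0.5.
- *False differences between active and placebo will be common across scales.* Over an assumed 4 scales correlated .5, unadjusted contrasts would give 16% (one active arm) or 26% (two). The plan specifies Scheffe, which brings these to about 5% and 9%.
- *LSD errors accumulate over three arms.* Compounding 16% gives 1 − .84³ = 41%, but this assumes that every visit comparison is run separately in each arm. The plan's only test described per arm is baseline v post-treatment.
- *LSD is certainly ungated.* The plan calls it post hoc and is silent on an omnibus condition. If it follows a significant omnibus F, the 16% falls to about 4%.

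**Conclusion.** The concern holds as a missing decision rule combined with ungated per-arm tests in unequal arms. If all arms change equally, significant improvement on full-spectrum CBD without significant improvement on placebo appears in about 2% of trials per scale at no change, 23% at 0.2, 52% at 0.4, 51% at 0.5, 18% at 0.8 and 5% at 1.0. These figures rest on a paired two-sided .05 test and an assumed shared change. Entry on a raised score makes a non-zero shared change plausible but does not fix its size.

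The arm imbalance drives the result and unadjusted testing adds to it. A reader might infer that replacing LSD with an adjusted procedure would be enough. It would not, because the 15-person arm would still have less power. The point should be settled before unblinding because it determines what the trial may conclude about efficacy.

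**What to change.** Before unblinding, amend Statistical Approaches as follows:

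1. Name one primary outcome, for example one of the anxiety scales already collected. The choice belongs to the investigators.
2. Name one primary test: full-spectrum v placebo at week 4, adjusted for baseline, alpha .05.
3. Test single-compound v placebo and the key secondary scales in a fixed order, or with Holm applied to the between-arm contrasts. Label everything else exploratory.
4. State that LSD and per-arm pre/post results are descriptive and support no efficacy conclusion.
5. Do not rely on Holm-adjusting the within-arm contrasts, for the reason shown in Step 4.

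The change is to SAP wording only and needs no further participants, visits or data. The downside is fewer nominally significant results. The 45 v 15 contrast also has only about 39% power for a 0.5 SD difference in change, and the plan should say so.
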